Part A Usability Study: Cross-sectional study comparing outcome variables for stroke survivors with varying levels of motor deficit impairment in their upper extremity. Subjects with mild motor deficits will be compared against stroke survivors with severe motor deficits after completing exercises with both commercial and custom therapy devices. Therapy exercises will be performed in random order, decided prior to the session. It will be randomly determined which robot the patient will use first, the order of operating modes used for the new robot, and the order of therapy exercises performed in each mode. Surface Electromyography (EMG) will be used in order to detect the small electric currents, or signals, which are generated by muscle activity. The collection of the strength and pattern of the signals will permit us to verify muscle activity over time. Part B Therapy Study: Pre-post study looking at change in outcome variables over 12 therapy sessions (three times a week for one month). Only low and mid functioning stroke survivors will be asked to participate in Part B of the study, and only the custom haptic device will be used by the study subjects. Pre-post evaluations will be administered at session 1 and 12. Surface Electromyography (EMG) will be used in order to detect the small electric currents, or

signals, which are generated by muscle activity. The collection of the strength and pattern of the signals will permit us to verify muscle activity over time.

Study duration

1) We estimate that it will take 3 years from the date of IRB approval to enroll all subjects and complete the study. 2) Part A - The subject's participation in the study will be limited to approximately 4 hours; 1-2 hours to be evaluated by a therapist with expertise in stroke rehabilitation and 2-3 hours of assessing the viability and usability of the various therapy devices. Part B - Subjects enrolled in Part B will be asked to return 3 times a week for 1 month (12 sessions). All sessions will last approximately 1.5 hours. 3) Projected date of the proposed study: 3/1/14 to 7/1/17.

Resources necessary for human research protection

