Part A: Participation in this part of the study will include the following steps: 1) Informed Consent: After arrival, subjects will review and sign the consent form with study personnel present. 2a) Pre-Assessments: A member of the research team will evaluate the subjects' affected arm and assess their ability to use it. Subjects will be evaluated using a battery of assessments in order to determine their level of impairment such as the Beck Depression Inventory, Upper Extremity Fugl-Meyer, Montreal Cognitive Assessment, Jebson Taylor, Box in Block, Modified Ashworth, and grip strength using a dynamometer, etc. 2b) Workspace Assessment: The protocol for the kinematic workspace would entail of moving patients upper extremity in a series of motions that mark the key points of their workspace. This would include movement with extended elbow to manipulate the shoulder joint in the cardinal directions (e.g. horizontal movements at the abdominal and shoulder levels, and vertical movements at 0, 45, 90 and 135 degrees), internal/external rotation of the shoulder, as well as functional movements of the arm. For the functional movements the patient would be asked to touch six points on their body, the left and right sides of their hips, their left and right shoulders, their mouth and the top of their head while being monitored by a Kinect camera. These actions are chosen as they cover areas necessary for ADLs such as eating, grooming and toileting and covers motion in clinically relevant planes. Each participant would be also given the standard clinical score. The movement protocols would be repeated under a loading condition where light weights (0.5-1lb) would be attached to subjects wrist. Given the additional mass, we would determine the change in the kinematic workspace space as well as the change in the joint torques. The protocol for recovery of dynamics would entail of the a series of motions using the TheraDrive systems as described in Theriault, A., Nagurka, M., Johnson, M.J: Therapeutic Potential of Haptic TheraDrive: An Affordable Robot/Computer System for Motivating Stroke rehabilitation, in: 5th IEEE RAS&EMBS International Conference, pp.415-420, 2014. The TheraDrive would be positioned at various locations in the subjects workspace (e.g. closer to the torso, away from the torso, higher/lower). The ability to exert specific torques at these locations would provide information on the dynamic capacity of the muscles within various points of the workspace. 3) Break:

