
Subjects will be given a 15 minute break. 4) First Therapy Device: Subjects will be introduced to several robots: a wheel, joystick, and custom crank chosen randomly (like the flip of a coin). First, they will be trained in the use of all robots and their safety features. Following training, they will be asked to move each robot into different positions, first without pressure applied to the handle, and then with pressure applied to the handle. After each exercise they will be asked about their level of exercise and level of pain discomfort. After subjects finish all exercises with a robot, they will be given a survey about the robot. They will also be given surveys to discuss their experience with the device and their level of motivation for use of them. The surface EMG may be utilized during the entirety of the participant's interaction with the novel therapy device. Prior to its placement on the subject, the reason for its use will be thoroughly explained. 5) Break: Subjects will be given a 15 minute break. 6) Subsequent Therapy Device: Subjects will be instructed in the use of another robot. The same procedure will be followed as in the first evaluation. The surface EMG may be utilized during the entirety of the participant's interaction with the novel therapy device. Prior to its placement on the subject, the reason for its use will be thoroughly explained. 7) Final Survey: Subjects will be given a survey asking them to evaluate the robots and indicate which robot they prefer. Part B: For subjects invited to participate in Part B of the study - only low functioning stroke survivors are eligible - participation in this part of the study will include the following steps: 1) Informed Consent: After arrival, subjects will review and sign the consent form with study personnel present. 2a) Pre-Assessments: If subjects are only participating in Part B of the study, at their first visit, a member of the research team will evaluate their affected arm and assess their ability to use it. Subjects will be evaluated using a battery of assessments in order to determine their level of impairment such as the Beck Depression Inventory, Upper Extremity Fugl-Meyer, Montreal Cognitive Assessment, Jebson Taylor, Box in Block, Modified Ashworth, and grip strength using a dynamometer, etc. If a study subject participated in Part A, they will not be reevaluated by a therapist. 2b) Workspace Assessment: Same as in Part A 2) Custom Therapy Device: Subjects will be introduced to the custom robot. They will be trained in the use of this robot and its safety features (1st session). Following training, they will be asked to move the robot into different positions. After each exercise subjects will be asked about their level of exercise and level of pain discomfort. Subjects will continue to work with the custom therapy device for 12 sessions over the course of one month. The surface EMG may be utilized during the entirety of the participant's interaction with the novel therapy device. Prior to its placement on the subject, the reason for its use will be thoroughly explained. 3) Motivation Questionnaire: At the end of their 1st and 12th sessions, subjects will be asked to complete a questionnaire assessing their level of motivation. 4) Post-Study Survey: After their last session, subjects will be asked to complete a survey assessing the robot. 5) Post-Study Assessment: After their last session, a certified therapist will evaluate the participants' affected arm and assess their ability to use it. In addition, they will also be evaluated for depression and a mental health assessment will be given.

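### Part B tests the arm before robot exercise at baseline but lists the final clinical evaluation after it, with no rest or interval specified before that final evaluation

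*Combined protocol and SAP*

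**What the plan says.** **Timing.** Study Design describes Part B as a single-group pre-post study over 12 sessions. It states: "Pre-post evaluations will be administered at session 1 and 12". It does not say where in the session the evaluations fall.

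**Baseline, Part B-only subjects.** Procedures, Part B, step 2a: "If subjects are only participating in Part B of the study, at their first visit, a member of the research team will evaluate" the affected arm. Robot training and exercise are listed afterwards.

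**Baseline, subjects from Part A.** The same step says: "If a study subject participated in Part A, they will not be reevaluated by a therapist". Their baseline is therefore the Part A battery, "2a) Pre-Assessments: A member of the research team will evaluate the" affected arm. In Part A the assessments are separated from the device work by a scheduled rest: "Subjects will be given a 15 minute break. 4) First Therapy Device".

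**End of Part B.** Step 3 gives the questionnaire: "At the end of their 1st and 12th sessions, subjects will be asked to complete a questionnaire assessing their level of motivation". Step 4 is the survey. Step 5 is "Post-Study Assessment: After their last session, a certified therapist will evaluate the" affected arm.

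**Duration.** Study duration, on Part B: "All sessions will last approximately 1.5 hours". An evaluation length of 1-2 hours is given for Part A only. Key exclusion criteria, item 3, requires Part B subjects to be able to sit for 2 hours at a time.

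**Fatigue.** Potential Study Risks says that intensity is held down partly because fatigue could confound the results, and that subjects will have plenty of rest. It fixes neither the length of the rest nor its place relative to the final evaluation.

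**The concern.** Fugl-Meyer and grip strength are among the primary outcomes, and both depend on what the affected arm can do when it is tested. If the arm is rested at baseline and has just been exercised at the end, the before-after difference contains the effect of that day's exercise as well as the effect of a month of therapy. With no comparison arm, the two cannot be separated.

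One stated purpose of the study is to learn whether low-functioning patients benefit and by how much. A clinical change measured under unequal conditions answers the second part poorly. It could make a useful device look weaker than it is when a follow-on study is planned.

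**Working it through.** The plan states no figure on this point, so the check is a comparison of the listed steps, followed by arithmetic on time.

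**1. Order of events**

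| | Baseline, Part B-only | Baseline, from Part A | Final evaluation |
|---|---|---|---|
| Where listed | Part B step 2a, first visit | Part A step 2a | Part B step 5, after the last session |
| Listed before it | Consent | Consent | Session 12 robot work, questionnaire, survey |
| Rest specified before it | Not needed | Not needed | None |
| Likely state of the arm | Rested | Rested | Exercised, if at the same visit |

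Both routes put the baseline battery ahead of robot work, and the final evaluation is the other way round. Since Study Design places the evaluation at session 12, the same visit is the likeliest reading. No day or interval is given, so it is not certain.

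**2. What the pre-post change contains**

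Let D be the true change over therapy, and F the effect of that day's prior exercise on the score (negative if fatigue lowers it). Then

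observed change = D + (F at end − F at baseline).

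Under the listed order F at baseline is about 0. If the final evaluation is on the same day and fatigue lowers scores, F at end is below 0. The observed change is then smaller than D. If the final evaluation is on a later day without exercise, F at end is also about 0 and the problem disappears.

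Putting a number on F would need a Part B sample size, a standard deviation of change and a fatigue effect. The documents give none of these.

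**3. Does the evaluation fit in the session?**

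Inputs: session of about 1.5 h; evaluation of 1-2 h (the Part A figure, assumed here to apply to Part B).

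- Inside the session: 1.5 − 1 = 0.5 h left for exercise; 1.5 − 2 = −0.5 h, so the longer evaluation does not fit.
- On top of a full session: 1.5 + 1 = 2.5 h to 1.5 + 2 = 3.5 h, beyond the 2 h of continuous sitting unless it is divided.
- Divided by a break: one block of 1-2 h and one of 1.5 h, each within 2 h.

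The documents do not settle which arrangement is meant.

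**4. Added time for the breaks**

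Total session time: 12 × 1.5 = 18 h. A 15-minute break at session 12 only (subjects from Part A): 0.25 / 18 = 1.4%. Breaks at sessions 1 and 12 (Part B-only subjects): 0.5 / 18 = 2.8%.

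**The case against.** The strongest reply is that the planners saw this confounder and acted on it. Potential Study Risks limits intensity because of fatigue, promises rest, and has subjects questioned after every exercise so that the work can be adjusted. It would be wrong to say that the protocol is silent on rest or on session length. This stands, and it narrows the point to one gap: none of these general controls is attached to the final evaluation. Part A schedules its 15-minute breaks as steps, whereas Part B lists none.

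Second, step 5 could mean a separate later visit. That also stands. Same-day fatigue is likely on the text but not established.

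Third, the clinical bias is conservative. A tired arm hides a gain; it does not create one. A reader might infer that the order could manufacture a clinical benefit, and the documents do not support that.

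A reader might also infer that tracking improvement is inflated, because session 1 tracking follows the battery and session 12 tracking precedes it. That goes further than the text allows. The Analysis Plan does not say when in session 1 the baseline tracking is taken. Nor is it clear that subjects from Part A escape arm work beforehand: they are excused from the therapist's evaluation, but step 2b, the workspace assessment with weighted movements and torque tasks, is not clearly waived. Any false-positive rate would rest on an invented sample size and an invented shift.

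**Conclusion.** The point holds in a limited form. The listed order itself creates a difference between baseline and final test conditions for the clinical outcomes, and no rest or interval before the final evaluation removes it. In a single-group pre-post study this goes straight into the estimated change.

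The likely direction is understatement of the clinical gain. The size is unknown and cannot be derived from the documents. The conclusion assumes that the final evaluation takes place at the session 12 visit, and that fatigue outweighs any warm-up effect on the scores. It does not depend on how the clinical scores are tested: the paired t-test is clearly assigned only to tracking accuracy, and the problem lies in the measured change itself.

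This does not invalidate the pilot. It is a weakness in measurement that is worth correcting because reordering a planned assessment is cheap.

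**What to change.** Add to Procedures, Part B:

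> The Part B clinical evaluation is done in a rested state before any robot exercise that day, both at baseline and at session 12, with a 15-minute break before robot work.

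Record the order and clock time of each test. Keep each sitting block within the 2 hours of Key exclusion criteria, item 3. State the expected length of the Part B evaluation. Until that length is given, do not declare evaluation time additional to the 1.5-hour session, because with the Part A figure that could add 1-2 h to an evaluation visit.

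**Costs**

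- The final clinical score reflects 11 of the 12 sessions.
- Session 12 tracking would follow the battery. For subjects from Part A, session 1 tracking may not have done so. This works against a tracking gain, and the break limits it.
- Breaks add about 15 minutes per evaluation visit, 1.4% to 2.8% of total session time.

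The reordering needs no extra visit, and eligibility, sample size and alpha stay as they are.

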Describe research staff and justify that the staff are adequate in number and qualifications to conduct the research. Describe how you will ensure that all staff assisting with the research are adequately informed about the protocol and their research related duties. Please allow adequate time for the researchers to conduct and complete the research. Please confirm that there are adequate facilities for the research.

All staff have taken the human subject certification and HIPAA training. The PI will have regular meetings with the research team to ensure that the team is adequately trained. We will recruit from our therapy services.

Characteristics of the Study Population

Target population

Stroke survivors greater than 18 years of age with hemiplegia and varying levels of impairment.

Subjects enrolled by Penn Researchers

56

Subjects enrolled by Collaborating Researchers

0

Accrual

Various Penn and Good Shepherd Penn Partners (GSPP) databases will allow the research team to search the respective systems within the parameters of the inclusion/exclusion criteria. Given the number of stroke survivors over the age of 18 with hemiplegia served by the Penn and GSPP community, recruitment of 56 (total for parts A, B) stroke survivors three months post event should be obtainable within the time frame specified. Justification for the sample size is based on the fact that this is a pilot study. Also, we expect that in Part A, not all willing participants will be able to continue post evaluation by a therapist (more than mild depression or cognitive impairment will be detected). Ideally, all low-functioning stroke subjects who participated in Part A would participate in B; however, we expect some attrition from the original group, requiring more subjects to be recruited. Subjects may also participate in Part A.

Key inclusion criteria

Part A: Stroke survivors greater than 18 years of age with hemiplegia and varying levels of impairment. The subject's stroke must have occurred at least 3 months prior to enrollment in the study. Part B: Low-functioning stroke survivors greater than 18 years of age with hemiplegia. The subject's stroke must have occurred at least 3 months prior to enrollment in the study.

Key exclusion criteria

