
The following documents are currently attached to this item:

There are no documents attached for this item.

Deception

Does your project use deception?

No

Analysis Plan

1) Clinical data will be analyzed to determine how subjects low versus high function perform on metrics developed using the robots. 2) Trajectory tracking using a baseline with zero resistance will be established for each patient. The root mean square metric will be used to assess accuracy in tracking tasks and subjects' performance across groups (low versus high) and devices in Part A, and across time in Part B. Using a 2-way ANOVA test for Part A, and an alpha of 0.05, significant difference across groups will be detected. A paired t-test, and an alpha of 0.05, will detect significant difference across time pre-post the 12 sessions. 3) Data collected from the surface EMG will be analyzed to verify muscle activity over time. 4) Data results will be used to build a simulation model of the human-robot tracking and determine a prediction of the joint and muscle forces that are used in Part A and Part B. 5) Data collected with the kinect will be assessed for kinematic and dynamic workspace. The data will be fitted to a computerized model of the upper limb to extract forces and positions defining dynamic and kinematic workspace.

The following documents are currently attached to this item:

There are no documents attached for this item.

Are you conducting research outside of the United States?

No

Data confidentiality

x Paper-based records will be kept in a secure location and only be accessible to personnel involved in the study.

x Computer-based files will only be made available to personnel involved in the study through the use of access privileges and passwords.

Prior to access to any study-related information, personnel will be required to sign statements agreeing to protect the security and confidentiality of identifiable information.

x Wherever feasible, identifiers will be removed from study-related information.

A Certificate of Confidentiality will be obtained, because the research could place the subject at risk of criminal or civil liability or cause damage to the subject's financial standing, employability, or liability.

A waiver of documentation of consent is being requested, because the only link between the subject and the study would be the consent document and the primary risk is a breach of confidentiality. (This is not an option for FDA-regulated research.)

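### Part B pools Part A continuers with direct recruits who may be new to the custom robot, and nothing separates device learning from therapy gain on the tracking outcome

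*Combined protocol and SAP*

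**What the plan says.** **Two routes into Part B.** The Accrual section gives the preferred route: "Ideally, all low-functioning stroke subjects who participated in Part A would participate in B". It then expects that some will not continue and that others will be enrolled: "we expect some attrition from the original group, requiring more subjects to be recruited". The Part B procedures confirm a Part-B-only route, with the arm assessed on entry: "If subjects are only participating in Part B of the study, at their first visit, a member of the research team will evaluate their affected".

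**Exposure to the custom robot.** Under Study Design, Part A subjects exercise on both commercial and custom devices. The Part A procedures train them on all the robots, including the custom crank, before the exercises. In Part B, the procedures introduce subjects to the custom robot at the start: "They will be trained in the use of this robot and its safety features (1st session"). Exercises follow that training.

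**Clinical baseline.** Study Design says: "Pre-post evaluations will be administered at session 1 and 12". The Part B procedures say: "If a study subject participated in Part A, they will not be reevaluated by a therapist".

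**Analysis.** Analysis Plan item 2 assesses RMS tracking accuracy across time in Part B and states: "A paired t-test, and an alpha of 0.05, will detect significant difference across time pre-post the 12 sessions". It also sets a zero-resistance tracking baseline for each patient, without saying when that is taken. It has no term, stratum or sensitivity analysis for entry route or earlier exposure. Part B has no control group.

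**The concern.** RMS tracking error on a robot falls as a person learns to operate the robot, whether or not the arm recovers. For a continuer, session-1 tracking comes after a Part A session with the device. For a direct recruit it may be first use. The same pre-post difference therefore measures two things: therapy plus whatever learning is left after Part A, and therapy plus learning from first contact.

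The plan reports one pooled change. If learning differs by route, that change depends partly on how many direct recruits were needed, a number the documents neither give nor ask to be reported. At stake is the reading of the Part B tracking result as evidence that low-functioning survivors gain from 12 sessions. Fugl-Meyer, ADL function and grip strength do not measure operation of the device and are less exposed.

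The clinical measures have a different problem. If Part A subjects are not re-evaluated, their 'pre' score dates from Part A, with no limit stated on the gap, while direct recruits are scored at their first Part B visit.

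**Working it through.** **No figure of the plan to reproduce.** The Accrual section gives 56 subjects for Parts A and B together and justifies this by pilot status. It gives no Part B number, attrition rate, SD, effect size or power. The calculation below only illustrates the mechanism.

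**Inputs**
- From the Analysis Plan: paired t-test, alpha 0.05. Sidedness is not stated; two-sided is assumed.
- Assumed: n = 20 in Part B; true therapy effect 0; paired differences normal with SD 1; learning gain Ln in new users and Lo in continuers, in SDs of the paired difference; fraction p of new users.

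**Formula.** The expected pooled change with no therapy effect is p × Ln + (1 − p) × Lo. The test statistic is t = mean difference / (SD / √n), and it rejects when |t| exceeds the 97.5% point of t with 19 degrees of freedom. Rejection rates come from simulation.

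| Learning assumed | p = 0 | 25% | 50% | 75% | 100% |
|---|---|---|---|---|---|
| Ln = 0.5, Lo = 0: mean shift | 0 | 0.125 | 0.25 | 0.375 | 0.5 |
| Ln = 0.5, Lo = 0: rejection | 5% | 8% | 17% | 34% | 56% |
| Ln = 0.5, Lo = 0.25: rejection | 18% | 26% | 35% | 45% | 56% |
| Ln = Lo = 0.5: rejection | 56% | 56% | 56% | 56% | 56% |

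Check of the last cell: with a uniform shift of 0.5, the noncentrality is 0.5 × √20 = 2.236, and the noncentral t distribution gives 56.4%.

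**Sensitivity to n**, with half the subjects new users, Ln = 0.5 and Lo = 0: 11% at n = 12, 17% at n = 20, 23% at n = 28.

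**Reading the table**
- The first scenario shows dependence on the mix, but its 5% at p = 0 holds only because continuers are assumed to learn nothing more.
- The last row shows that learning contaminates the test fully with a single route. Mixing adds a second problem: the size of the contamination varies with an unreported share.
- Reporting by route exposes a difference between routes. It does not remove learning that both share.

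**Selection.** A separate simulation chose subjects on a low first score. With a fresh baseline, the mean pre-post change was 0.00, so selection before the baseline does not create change. If the score used for selection is reused as baseline, regression to the mean adds about 0.05 to 0.37 SD of the difference, for assumed reliabilities of 0.98 to 0.80 and cut-offs from +0.5 to −0.5 SD. The documents do not say which measure defines low function, so this is only a reason to settle the baseline rule.

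**Baseline passages side by side.** Study Design places the pre evaluation at session 1 for Part B. The procedures exempt Part A subjects from therapist re-evaluation. For continuers both cannot hold.

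**The case against.** Several points on the other side stand.

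- Learning affects any single-group pre-post tracking measure, so replacement is not its cause. Nothing in the documents says that continuers have finished learning after a Part A session shared among several devices. This stands.
- The number in Part B, the learning gain and the share of new users are all assumptions. This stands; the table shows direction and sensitivity only.
- The Accrual section says that subjects may also take part in Part A, so added recruits are not all new to the robot. The plan does not state that the routes are pooled; that is inferred from the single test. Both are true, and uncertain exposure is itself a reason to record it.
- The plan has session-1 training and a zero-resistance baseline. These help in part, but the training has no fixed amount of practice, and neither is placed in time relative to the 'pre' tracking measure.

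A reader might go further and infer that selective continuation itself appears as therapy effect, because people who disliked the robot or found it painful leave and are replaced. The documents do not support this. Continuation is decided before a Part B baseline taken at session 1, so it changes whom the result applies to and not the within-subject change. No passage links attrition or invitation to pain or dislike. The invitation sentence, "For subjects invited to participate in Part B of the study - only low functioning stroke survivors are eligible", ties entry to functional level. Part A also surveys its subjects about the robots before anyone could leave for this reason, so the Part A usability data are not selected by continuation.

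**Conclusion.** The point holds in limited form. Part B combines two entry routes that can differ in prior use of the custom robot and, for clinical scores, in when the baseline is taken. The single uncontrolled paired t-test does not separate them, and no practice is fixed before the 'pre' tracking measure. Device learning can therefore be counted as therapy gain on RMS tracking, by an amount that differs by route when learning differs.

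With n = 20, no therapy effect and 0.5 SD of learning in new users only, false rejection rises from about 5% to 56% as the share of new users goes from none to all. With equal learning it is about 56% at any mix. These sizes rest on assumed values. The structural point does not: it follows from the text.

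Pilot status excuses low power, but it does not excuse a baseline that means different things for different subjects. The changes are cheap and worth making.

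**What to change.** 1. Take the Part B 'pre' tracking measure at session 1, after the device training plus the same fixed practice block for every participant, whatever the entry route. State when the zero-resistance baseline is taken relative to it.
2. Record prior use of the custom robot. Report tracking change for Part A continuers and direct recruits beside the pooled result, and state that the change includes any remaining learning.
3. Reconcile the Study Design statement on pre-post evaluation at sessions 1 and 12 with the procedures' statement that Part A subjects are not re-evaluated, so that the clinical baseline is defined the same way for both routes.
4. Tabulate low-functioning Part A subjects who continued against those who did not, using their existing Part A pain ratings, surveys and tracking. Present this as a statement of generalisability only.

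**Cost.** Items 2 and 4 use data the plan already collects, apart from recording entry route and prior use. Item 1 adds a short practice block to session 1. Item 3 is wording, plus a repeat clinical assessment of continuers if it is resolved that way. Estimates by route will be imprecise in a small sample and should be shown descriptively. A practice block reduces learning but cannot remove it; full separation would need a control group.
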